Record concomitant medication since last visit		Х	х	х		Х	х	х	Х		х	х	х		х	х	х	х
Blood draws for humoral response assessments h		X f 30 mL					X f 30 mL		X 30 mL		X 30 mL	X f 30 mL	X 30 mL		X 30 mL	X 30 mL	X 30 mL	X 30 mL
CCI																		
Blood draw for genetics		X ^f 4 mL																

Page 10 of 82 Version: 4.0 Date: 13 FEB 2023

Activity	Visit (V) 0	V 1	V 2	V 3	VS1 (Call)	V 4 (Call)	V 5	V 6	V 7	V S 2 (Call) ^p	V 8	V 9	V 10	VS3 (Call) P	V 11	V 12	V 13	V 14
Visit description	Screen ing	Dose (D) 1 (Day 1)	1 d FU post- D 1	7 d FU post- D 1	(14 d post- D 1)	28 d FU post- D 1	D 2 (Day 5 7)	1 d FU post- D 2	7 d FU post- D 2	(14 d post- D 2)	28 d FU post- D 2	D 3 (Day 1 83)	7 d FU post- D 3	(14 d post- D 3)	28 d FU post- D 3	84 d FU post- D 3	168 d FU post-D 3	365 d FU post-D 3 or ET
Visit window	-30 to -	N/A	±4 h	+2 d	+1 d	±2 d	±2 d	±4 h	+2 d	+1 d	±2 d	±7 d	+2 d	+1 d	±2 d	±10 d	±10 d	±10 d
CCI																		
Subject hotline availability	Start	=>	=>	=>		=>	=>	=>	=>		=>	=>	=>		=>	=>	=>	End
Issue, train and collect subject e-diaries		Issue, train ⁱ					Re- train ⁱ					Re- train ⁱ	Collect					
Subjects report reactogenicity (incl. oral body temperature) daily for 7 d after each IMP dose using an e-diary		Start after Dose 1	=>	End ⁿ			Start after Dose 2	=>	End ⁿ			Start after Dose 3	End ⁿ					
Investigators review e-diary data daily		Start	=>	End			Start	=>	End			Start	End					
Record AEs, MAAEs, and SAEs ^j		х	х	х		Х	х	х	х		х	х	х		х	х	х	х
Wellbeing phone call		X k			X۰		X k			Χ°		X k		Χ°				
Investigator local reaction assessment		Χ¹					Χ¹					Χ¹						

Page 11 of 82
Version: 4.0
Date: 13 FEB 2023

Activity	Visit (V) 0	V 1	V 2	V 3	VS1 (Call)	V 4 (Call)	V 5	V 6	V 7	V S 2 (Call) ^p	V 8	V 9	V 10	V S 3 (Call) ^p	V 11	V 12	V 13	V 14
Visit description	Screen ing	Dose (D) 1 (Day 1)	1 d FU post- D 1	7 d FU post- D 1	(14 d post- D 1)	28 d FU post- D 1	D 2 (Day 5 7)	1 d FU post- D 2	7 d FU post- D 2	(14 d post- D 2)	28 d FU post- D 2	D 3 (Day 1 83)	7 d FU post- D 3	(14 d post- D 3)	28 d FU post- D 3	84 d FU post- D 3	168 d FU post-D 3	365 d FU post-D 3 or ET
Visit window	-30 to - 1 d	N/A	±4 h	+2 d	+1 d	±2 d	±2 d	±4 h	+2 d	+1 d	±2 d	±7 d	+2 d	+1 d	±2 d	±10 d	±10 d	±10 d
Cumulative blood volume (mL)	20	164	10	70		0	150	10	160		140	155	155		140	140	140	140

- a Brief (symptom-orientated) physical examination.
- b Before (up to 1 h) dosing and at 1 h (±15 minutes) after dosing.

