- c Vital signs: systolic/diastolic blood pressure, pulse rate, respiratory rate, and oral body temperature.
- d Viral screen: screen for HIV 1, HIV 2, Hepatitis B, and Hepatitis C.
- e Clinical laboratory tests: (Chemistry) alkaline phosphatase, alanine transaminase, creatinine, c-reactive protein, albumin, amylase, aspartate transaminase, gamma glutamyl transpeptidase, total bilirubin, blood urea nitrogen, glucose, lipase, sodium, potassium, calcium, troponin, IgG, IgM and IgA; (Hematology) hemoglobin, hematocrit, red blood cell count, white blood cell count and differential (neutrophils, lymphocytes, monocytes, eosinophils, basophils), platelet count. Only in women who are not VOCBP (to confirm postmenopausal status): follicle stimulating hormone at Visit 0. Only for VOCBP: serum β-HCG at Visit 0.
- f On days with dosing, blood draws should be done pre-dose.
- g VOCBP: The serum β-HCG pregnancy test at Visit 0 is performed using the sample collected for clinical laboratory tests. Before each dosing, urine pregnancy tests will be performed using a commercial kit at the site and the trial subjects will be counseled about the need for consistent and correct use a highly effective method of contraception.
- h If justified by the collected data, the listed blood draw days and the draw volumes may be adapted if not increasing the total number of draw days or the total volume drawn. Leftover blood after completion of the immunogenicity assessments may be used for additional biomarker analyses.
- i Trial site personnel will remind the subjects to record the oral body temperature and the worst grade for each symptom in the e-diary at approximately the same time every evening on the day of IMP administration and then every day in the evening for a total of seven consecutive days. Ask/remind the subject to contact the site if they experience any severe or potentially life-threatening reactogenicity events.
- The AEs and MAAEs will be collected continuously until 28 d after each dose, and SAEs need to be recorded continuously until Visit 14.
- k Trial subjects will be contacted by phone for non-leading wellbeing calls at 5 h, 24±4 h (after Dose 3 only), and 48±4 h after each IMP dose.
- I Local reactogenicity assessed by the investigator pre-dose and up to 1 h after dosing.
- m 12-lead ECG will be performed pre-dose.
- n Subjects will make their last entries in the evening before the 7 d follow-up visit.

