- o Trial subjects will be contacted by phone for wellbeing calls at 14 (+1) d after each IMP dose and to solicit local injection site reactions starting after 7 d and through 14 d post-IMP administration.
- p Local reactogenicity calls after 14 d.

Clinical Trial Protocol
Trial number: BNT165-01

Page 12 of 82 Version: 4.0 Date: 13 FEB 2023

Notes:

If, for any reason subjects are permanently discontinued from the trial before completing all scheduled visits, if possible, all assessments planned for the actual week or day of that visit as listed in the SoA, should be performed, at minimum, all assessments scheduled at Visit 14 should be performed. The only exception is pregnant women who will not have further research blood draws, but will otherwise complete planned assessments.

The total blood volume drawn over any 8-week period in any cohort will always be less than 550 mL. Additional blood samples may be taken, e.g., for safety assessments after AEs or SAEs. The total volume of blood drawn from each subject over 546 d will be up to ~1,594 mL.

Abbreviations: AE = adverse event; COVID-19 = Coronavirus Disease 2019; d = day(s); ECG = electrocardiogram; ET = early termination; FU = follow-up (visit); h = hour(s); β-HCG = beta human chorionic gonadotropin; HIV = human immunodeficiency virus; IMP = investigation medicinal product; Ig = immunoglobulin; MAAE = medically attended adverse event; RNA = ribonucleic acid; SARS-CoV-2 = Severe acute respiratory syndrome coronavirus type 2; SAE = serious adverse event; SoA = schedule of activities; VOCBP = volunteers of childbearing potential.

Clinical Trial Protocol Trial number: BNT165-01

Page 13 of 82 Version: 4.0 Date: 13 FEB 2023

TABLE OF CONTENTS

1	PROTOCOL SYNOPSIS	2
1.1	Summary	2
1.2	Schema (graphical representation of the trial)	7
1.3	Schedule of activities	8
TABLE	OF CONTENTS	13
LIST OF	TABLES	16
LIST OF	FIGURES	17
ABBRE	VIATIONS/TERMS	18
2	INTRODUCTION	20
2.1	Background	20
2.1.1	The medical need	20
2.1.2	Clinical development of a BioNTech multi-antigen vaccine	21
2.2	Trial rationale	22
2.3	Benefit/risk assessment	23
2.3.1	Benefit assessment	23
2.3.2	Risk assessment	23
2.3.3	Risk mitigation	24
2.3.4	Overall benefit/risk conclusion	24
3	OBJECTIVES AND ENDPOINTS	25
4	TRIAL DESIGN	26
4.1	Overall design	26
4.1.1	Planned number of trial subjects	26
4.1.2	Duration of all trial periods	27
4.2	Scientific rationale for the trial design	27
4.3	Justification for the trial treatment	27
5	TRIAL POPULATION	28

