7.1.3 Permanent discontinuation of trial treatment

Trial treatment administration will be permanently discontinued for an individual trial subject if any of the below criteria are met.

- Any Grade 4 reactogenicity event considered to be possibly related
- Pregnancy
- Any severe acute systemic hypersensitivity AE or anaphylactic reaction of Grade 3 or above assessed as possibly related to IMP
- Any suspected or confirmed immune-related AE, including but not limited to myocarditis or pericarditis assessed as possibly related to IMP

Clinical Trial Protocol Trial number: BNT165-01 Page 41 of 82 Version: 4.0 Date: 13 FEB 2023

After pausing trial treatment according to Sections 7.1.1 and 7.1.2, the IRC may recommend a permanent discontinuation of trial treatment overall, in a cohort, or for a single trial subject.

A permanent discontinuation of trial treatment may also occur for non-medical reasons at the judgment of the investigator or the subject (i.e., subject moves to a new location).

Trial subjects permanently discontinued from trial treatment will complete all assessments planned for the actual week or day of that visit as listed in the SoA (Section 1.3), at minimum, all assessments scheduled at Visit 14 should be performed. The only exception is pregnant women who will not have further blood draws, but will otherwise complete planned assessments, if required including pregnancy follow-up until birth.

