8.12 Early termination visit(s)

If, for any reason, subjects are permanently discontinued from the trial before completing all scheduled visits, subjects will complete an Early Termination Visit. If possible, all assessments planned for the actual week or day of that visit as listed in the SoA (Section 1.3) should be performed.

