12.2 Management of risks associated with anemia

This trial limits the total volume drawn over each sequential 8 week period to less than 550 mL, however, if a trial subject develops anemia, they should be evaluated and treated with iron supplements if appropriate.

If the trial subject develops Grade 3 anemia, the volume of blood drawn at any visit will be kept to a minimum, i.e., may be reduced to only safety assessments, at the discretion of the investigator.

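### The 550 mL per 8 weeks blood limit holds on schedule, but the early-termination minimum in the schedule note would exceed it (600 or 590 mL) if followed about 27–55 days after Dose 2 or Dose 3

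*Protocol*

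**What the plan says.** **The limit.** The note under Table 1 in Protocol 1.3 states: "The total blood volume drawn over any 8-week period in any cohort will always be less than 550 mL". Section 8.9 repeats the sentence. Section 12.2 restates it under anemia risk: "This trial limits the total volume drawn over each sequential 8 week period to less than 550 mL".

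**The early-termination minimum.** The paragraph just before the limit, in the same note, covers subjects permanently discontinued from the trial. If possible, they have what is planned for that day or week and, "at minimum, all assessments scheduled at Visit 14 should be performed". The one exception named is pregnancy, after which no research blood is drawn. The Visit 14 column is headed "365 d FU post-D 3 or ET" and its volume entry is 140 mL. SAP Appendix 4 reproduces the table and the note.

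**Related text.**
- Section 8.12: "subjects will complete an Early Termination Visit". It then asks, if possible, only for the assessments planned for that day or week. Section 7.2 refers to 8.12. Neither contains the Visit 14 minimum.
- Section 7.1.3, on stopping trial treatment, asks for assessments "as listed in the SoA (Section 1.3), at minimum, all assessments scheduled at Visit 14 should be performed". It omits the if-possible qualifier and gives no time for doing them.
- Footnote h says "the draw volumes may be adapted if not increasing the total number of draw days or the total volume drawn", on condition that collected data justify it. In the visible table it is attached to the 30 mL humoral row.
- Section 12.2: "If the trial subject develops Grade 3 anemia, the volume of blood drawn at any visit will be kept to a minimum", at the investigator's discretion.

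**The concern.** The limit is stated without exception. The Visit 14 set is stated as a floor with one exception. An early-termination visit has no fixed date, so it can fall soon after the cluster of draws that follows a dose, and the visible text does not say which statement then prevails.

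What is at stake is subject protection. The limit is the protocol's stated safeguard against blood loss in healthy volunteers, and Section 12.2 relies on it. A site that follows the early-termination request in full at the wrong time would exceed it.

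**Working it through.** **Inputs.** Volumes are from the last row of Table 1 (Protocol 1.3); days are nominal, with doses on Days 1, 57 and 183.

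| Visit | Day | mL |
|---|---|---|
| V0 | screening | 20 |
| V1 | 1 | 164 |
| V2 | 2 | 10 |
| V3 | 8 | 70 |
| V4 | call | 0 |
| V5 | 57 | 150 |
| V6 | 58 | 10 |
| V7 | 64 | 160 |
| V8 | 85 | 140 |
| V9 | 183 | 155 |
| V10 | 190 | 155 |
| V11 | 211 | 140 |
| V12, V13 | later follow-up | 140 each |
| V14 or ET | 365 d after Dose 3, or at early termination | 140 |

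**1. The protocol's own total.** The row is labelled cumulative, but its entries sum to 20 + 164 + 10 + 70 + 0 + 150 + 10 + 160 + 140 + 155 + 155 + 4 × 140 = 1,594 mL, which is the stated total. They are therefore per-visit volumes that already include the redacted rows.

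**2. On schedule.** The largest sum over any 56 consecutive days is V5 to V8: 150 + 10 + 160 + 140 = 460 mL. V9 to V11 gives 155 + 155 + 140 = 450 mL. Moving visits within their allowed windows does not raise the maximum. The limit holds.

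**3. With a 140 mL early-termination (ET) draw.**
- After V8 and within 8 weeks of Dose 2: 460 + 140 = 600 mL, for ET on Days 86–112.
- After V11 and within 8 weeks of Dose 3: 450 + 140 = 590 mL, for ET on Days 212–238.

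Allowing for the visit windows, both cases are ET 27–55 days after the dose (27–56 if 8 weeks is counted as 57 inclusive days).

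**4. Other ET times.** On nominal days the sum is at most 460 mL. At the edges of the visit windows it can reach 70 + 150 + 10 + 160 + 140 = 530 mL (V3, V5, V6, V7, ET). Counting 57 inclusive days, it can reach 164 + 10 + 70 + 150 + 10 + 140 = 544 mL (V1, V2, V3, V5, V6, ET). Both are below 550 mL. If ET coincides with V8 or V11, the totals stay at 460 and 450 mL.

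**5. Fixed 8-week blocks.** If Section 12.2 means consecutive 56-day blocks from Day 1, the excess remains on Days 86–112 (600 mL) and 212–224 (590 mL).

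**6. How much must be left out.** The ET draw must be below 550 − 460 = 90 mL after Dose 2 and below 550 − 450 = 100 mL after Dose 3. Dropping only the visible 30 mL humoral tube leaves 570 or 560 mL.

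**7. How many subjects.** The documents give no dropout rate. Assume 5–15% of 60 subjects (3 to 9) leave, evenly over 546 days, and all give the full ET draw. The two windows cover 27 + 27 = 54 days, so the expected number is 3 × 54/546 = 0.30 to 9 × 54/546 = 0.89. With fixed blocks (27 + 13 = 40 days) it is 0.22 to 0.66. These are upper bounds, because subjects lost to follow-up or refusing the visit give no blood.

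**The case against.** The strongest reply is that the wording already ranks the two statements. The limit is categorical; the Visit 14 request is hedged by *if possible* and *should*. A site can draw fewer research tubes and satisfy both. This stands in part: the protocol does not compel a breach, and no printed figure is wrong. But a set described as a minimum, with a single named exception, reads as a floor, and a site would have to notice the clash itself.

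Three stronger readings are tempting, and the documents do not support them.
- *The planned schedule breaks the limit.* It does not; the maximum is 460 mL.
- *Section 8.12 requires the 140 mL draw.* It requires the visit, but asks only, if possible, for what is planned that day or week. Nominally no blood draw is planned between V8 and V9, or between V11 and V12. The conflict comes from the schedule note and the column heading.
- *Section 7.1.3 is a second breach.* It gives no timing. If the assessments are done when treatment is stopped on Days 86–112, the total is again 600 mL. If the subject stays in follow-up and has Visit 14 on its date, there is no excess.

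Two provisions might be thought to resolve the matter. Footnote h may also apply to redacted rows, which hold the other 110 mL, so its full reach cannot be judged; its condition about collected data would still apply. The sentence allowing additional samples has an open list, but its example is safety sampling after adverse events, and the ET draw is a scheduled column with a printed volume. Section 12.2's reduction applies only to Grade 3 anemia.

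**Conclusion.** The point holds as a narrow inconsistency within the schedule note, and it is minor. Following the Visit 14 minimum at an early termination about 27–55 days after Dose 2 or Dose 3 puts the 8-week total 50 or 40 mL above a figure it is promised to stay below. The two totals rest only on printed volumes and visit days. The number affected, probably fewer than one subject, rests on the assumed dropout rate and on full attendance at the ET visit. No endpoint, analysis or dose-escalation decision depends on it.

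**What to change.** Keep the limit. At the next amendment, add to the schedule note and to Section 8.9:

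*The 550 mL limit takes precedence over the Visit 14 minimum: at an early-termination visit, research blood draws are reduced or omitted as needed so that the total over the preceding 8 weeks, including that visit, stays below 550 mL.*

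Cross-reference it in Sections 7.1.3 and 8.12. If numeric caps are wanted, bound them in time: below 90 mL for ET after V8 and within 8 weeks of Dose 2, and below 100 mL for ET after V11 and within 8 weeks of Dose 3. Without that bound they would restrict later visits where there is no excess.

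The cost is one sentence in two places, two cross-references, and the loss of some exploratory samples in subjects recently sampled at V8 or V11. The visible clinical-laboratory row has no draw at Visit 14, so no scheduled safety test shown in the table is lost; the content of the redacted rows cannot be checked.

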2 INTRODUCTION

2.1 Background

2.1.1 The medical need

Malaria is a serious and sometimes fatal disease caused by a parasite that commonly infects a certain type of mosquito (*Anopheles* mosquito) which feeds on humans. Typical symptoms of a malaria infection in humans are high fever, shaking chills, and flu-like illness. Compared to malaria caused by other *Plasmodium* species, *P. falciparum* malaria is the type that is most likely to result in severe infections and, if not promptly treated, may lead to death.

The WHO estimated that there were ~241 million cases of malaria and 627,000 malaria -associated deaths in 2020, of which 98% are caused by the parasite *P. falciparum*, and 95% of cases occur in the African region (WHO Malaria Report 2021). The WHO has stated the goal to reduce the incidence and mortality due to malaria by 90% until 2030.

Despite programmatic efforts, recent gains to decrease malaria morbidity and mortality have been partially reversed, underscoring the need for effective malaria vaccines and other new tools to prevent malaria and achieve the WHO goals. Medicines based on artemisinin have improved the treatment options for malaria and vector control and exposure control programs have led to large reductions in malaria incidence. However, progress has stalled recently, and has even reversed during the Coronavirus Disease 2019 (COVID-19) pandemic.

Additionally, there is a risk of development of biological resistance against insecticides and antimalarial treatments. Effective vaccines preventing malaria caused by *P. falciparum* are urgently needed to achieve the goal of malaria eradication and to reduce the physical and socioeconomic burden of malaria in highly endemic areas.

Children in highly malaria endemic countries may experience multiple malaria episodes in their lives – all associated with a risk of severe disease, chronic complications, or death. While effective treatment exists, this may not always be available in remote areas and travel to the next health center is often very cumbersome. Preventing these malaria episodes with highly effective vaccines would reduce the individual disease and economic burden on children and their families. Pregnant women and people living with human immunodeficiency virus (HIV) in endemic areas, are both special populations at higher risk of clinical malaria and malaria-associated complications while adults in endemic areas who can be parasitemic but asymptomatic, act as a reservoir for ongoing transmission. A highly effective vaccine preventing blood stage infection may therefore decrease disease and onward transmission.

In non-endemic countries, where the number of malaria cases are comparatively low, the vast majority of malaria cases are imported from malaria endemic areas by tourists, migrant workers or immigrants returning from visiting friends and relatives. Travelers can protect themselves from malaria by taking chemoprophylaxis (e.g., atovaquone/proguanil, doxycycline, mefloquine), however, this may be impractical for prolonged stays. Ultimately

Clinical Trial Protocol Trial number: BNT165-01 Page 21 of 82 Version: 4.0 Date: 13 FEB 2023

over 90% of imported malaria cases occur in individuals who did not take or incorrectly applied chemoprophylaxis. A highly efficacious long-lasting malaria vaccine could also help prevent imported malaria cases.

The world's first approved malaria vaccine is an adjuvanted protein subunit vaccine that consists of the major repeat region and the C-terminus of the *Pf*CSP fused to the Hepatitis B surface antigen (HBsAg). The vaccine is a mix of this *Pf*CSP-HBsAg compound with HBsAg that forms virus-like particles (RTS,S/AS01; Mosquirix™). Phase III studies of RTS,S delivered as a 3-dose series with a booster after 1 year showed moderate vaccine efficacy in children aged 5 to 17 months preventing 36% of clinical malaria cases over the full study period with a median follow-up of 4 years, with a range of 20% in high to 66% in low transmission settings. Furthermore, published literature suggests that protection wanes over time including reports of potential negative efficacy after 5 years in children with high malaria exposure (Olotu et al. 2016).

2.1.2 Clinical development of a BioNTech multi-antigen vaccine

P. falciparum is transmitted when an infected *Anopheles* mosquito bites the human host and injects sporozoites into the skin. Within at most a few hours, the sporozoites travel via the bloodstream to the liver (pre-erythrocytic stage). After hepatocyte invasion the parasite multiplies over 7 to 10 d (liver stage), before the *P. falciparum* merozoites are released into the human host bloodstream and infect erythrocytes (blood stage).

Circumsporozoite protein (CSP) is the major surface antigen of sporozoites. Antibodies targeting CSP have been shown to neutralize sporozoites and to reduce malaria morbidity and mortality. The approved malaria vaccine RTS,S/A01 also consists of a fragment of CSP that includes 18 central NANP repeats as well as the C-terminus of CSP. A monoclonal antibody (CIS43LS) that binds preferentially to the junctional NPDP epitope has recently shown 100% protection in a human malaria challenge model (Gaudinski et al. 2021). Similarly, the monoclonal antibody L9 which in addition to binding to NANP repeats shows high avidity to NVDP repeats, mediates protection in a murine malaria challenge model (Wang et al. 2020). Vaccines eliciting antibodies similar to these monoclonal antibodies may therefore provide superior protection compared to RTS,S (Moon et al. 2020; RTS,S Clinical Trials Partnership 2015). Additionally, the durability of the anti-CSP immune response may be different when using an RNA-based approach and will be assessed.

A single sporozoite is sufficient to allow hepatocyte invasion and further development into the blood stage, at which point anti-CSP antibodies are not functional anymore. Targeting one or more other life cycle stages in addition to the sporozoites may therefore increase the likelihood of preventing blood stage infection and provide a higher vaccine efficacy, as parasites evading the anti-CSP response will face an additional immunological hurdle.

The rationale for the multi-antigen design is to build upon the success of RTS,S by (a) first improving the CSP antigen used in RTS,S and (b) adding additional antigens that target different parts of the *P. falciparum* life cycle to drive both B- and T-cell responses. The goal is to make a safe vaccine with higher efficacy, durability and suitability for use in different populations.

Clinical Trial Protocol Trial number: BNT165-01 Page 22 of 82 Version: 4.0 Date: 13 FEB 2023

The BNT165 clinical development will begin with this FIH, dose escalation trial designed to assess the safety, tolerability, and immunogenicity of the vaccine component BNT165b1, that focuses on generating an immune response against a region of *Pf*CSP not included in RTS,S. Later other vaccine components that encode distinct regions of *Pf*CSP or the full length *Pf*CSP, or antigens associated with other *P. falciparum* life cycle stages and/or combinations thereof, will also be assessed. The final composition of the BNT165 multi-antigen vaccine will be defined based on aggregate data from pre-clinical studies and clinical testing of the components (used alone or in combination) before progressing into Phase II/III clinical development.

If vaccine components like BNT165b1 are well tolerated in the BNT165-01 clinical trial, BioNTech may investigate them alone or in combination in a Phase IIa proof of concept trial assessing protection against a human malaria (i.e., in a human malaria challenge model).

